Japanese healthy elderly subjects and healthy adult male subjects received multiple doses (0.5 mg/kg, twice daily for 2 days), after which the PK and safety were evaluated. Following multiple doses of 30-minute IV infusion, the PK course of the unchanged drug and the metabolites in plasma were similar for the elderly subjects and adult male subjects, and no particular changes were observed in the urinary excretion. No particular differences were found in safety between the elderly and adult male subjects. In addition, no clinically significant findings were observed. In the clinical study to evaluate effects of edaravone on the QT/QTc interval in healthy adult male subjects (MCI-186-J25), C_{max} and $AUC_{0-\infty}$ were 1,195 ng/mL and 1,738 ng·hr/mL, respectively after 60 mg/60 min edaravone IV infusion, which is the dose approved for ALS treatment.

The population PK analysis was performed by use of the PK data from the 5 clinical pharmacology studies of edaravone IV administration to healthy adult subjects in Japan and Europe. As a result, no particular differences were observed in the PK profiles between Japanese and Caucasians by race, sex, age, or body weight.

In the phase I study (MT-1186-J01 study) of oral edaravone in healthy adult males, 74 subjects (54 in the edaravone group, 20 in the placebo group) received single (Cohort S1 to S7) or 5-day repeated administration (Cohort M1 and M2) of oral edaravone solution or oral suspension at doses of 30 to 300 mg, and PK, safety and tolerability were examined. In addition, effects of the race and meal were examined at a dose of 200 mg.

In terms of safety, no serious adverse events occurred. A total of 21 adverse events were observed in 74 subjects. Among them, the only adverse event assessed as causally related to the administration was headache (1 event) in the edaravone group. The event was mild in severity and rapidly resolved. One subject in the edaravone group discontinued the study owing to adverse events. In the meal-effect cohort, moderate conjunctivitis occurred after administration of Cohort S3-1 (200 mg, a single dose in the fasting state), and administration of S3-2 (30 minutes after meal) was called off. This event was considered not related to the investigational product.

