8.6.1 Hospitalization and Visits

- (1) The subjects will visit the study site on the specified days for screening, hospital admission and end-of-study assessment.
- (2) The subjects will visit the study site in the fasting state from at least 10 hours before blood sampling on the days of screening, hospitalization, and end-of-study assessment. (They can have food after completion of the prescribed tests.)
- (3) Hospitalization period: Period I-IV: 10 days and 9 nights (Day -1 to Day 9),
Period V: 4 days and 3 nights (Day X to Day X+3) (X = Day of hospital admission in period V)

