9.2.3 Treatment compliance

The investigator (or subinvestigator) or study collaborator will record the date and time of investigational product administration in the CRF.

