9.2.5.1 Objective findings

The investigator (or subinvestigator) will check for results of all of the following tests without delay.

Confidential

The investigator (or subinvestigator) or study collaborator will record the dates and times of measurement and blood/urine sampling in the CRF.

(1) General laboratory tests

The following test items will be measured. The approximate blood volume per sampling is approximately 2 mL for the following 1), 6 mL for 2), 1.8 mL for 3), and 6 mL for 5), described below. The investigator (or subinvestigator) or study collaborator will provide the sponsor with electronic data on the measurement results (except for the result of coagulation test and hCG) of the subjects who received the investigational product. Blood will be collected in the fasting state.

1) Hematology:

Hemoglobin, hematocrit, red blood cell count, white blood cell count, platelet count, MCH, MCHC, MCV, differential white blood count

2) Biochemistry:

Na, K, Cl, Ca, inorganic phosphorus, urea nitrogen, creatinine, uric acid, total bilirubin, direct bilirubin, ALT, AST, γ -GTP, ALP, LDH, CK, amylase, total cholesterol, triglycerides, LDL-C, HDL-C, total protein, albumin, glucose

3) Coagulation test:

Prothrombin time, activated partial thromboplastin time

4) Urinalysis (qualitative test):

Sediment, qualitative tests (pH, specific gravity, protein, glucose, occult blood, urobilinogen, bilirubin, ketones)

hCG (performed only for female subjects at screening, on Day -1 (hospitalization), and at the end-of-study assessment)

Time points: To be performed in the fasting state at the following time point (before breakfast).

Screening	No specifications
Day -1 (hospitalization)	No specifications
Day 5	Pre-dose
Day 9 (discharge)	Before breakfast
Day X ^{a)} (hospitalization)	No specifications
Day X+3 ^{a)} (discharge)	Before breakfast
End-of-study assessment or withdrawal assessment	No specifications

a) X = Day of hospital admission in period V

Frequency of blood sampling: 7

Total blood sampling volume: 74.6 mL (for details, see "9.3 Blood Sampling Volume")

(2) Vital signs (blood pressure, pulse rate, body temperature)

Systolic and diastolic blood pressure, pulse rate, and axillary body temperature (in Celsius; rounded to one decimal place) of each subject will be measured at the time points shown in the table below. The investigator (or subinvestigator) or study collaborator will record the date, time, and results of the measurement in the CRF.

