3.2. Study Design

3.2.1. Type and Details of Cohorts

Single-dose, randomization, open-label, crossover study

Group	Period I (at Day 1)	Period II (at Day 3)	Period III (at Day 5)	Period IV (at Day 7)	Period V (at Day X+1)
1	A	B	C	D	The diet condition will be determined based on the PK data collected from period I to period IV. *) (E, F, or G etc.)
2	B	C	D	A	
3	C	D	A	B	
4	D	A	B	C	

A: Dosing under fasted condition

B: Dosing 8 hours after high-fat meal

C: Dosing 4 hours after low-fat meal

[figure not shown]
D: Dosing 2 hours after light meal

*) The diet menu (any one of high-fat meal, low-fat meal and light meal) and dosing time after a meal (within a range of 30 minutes to 10 hours after a meal) in period V will be determined based on the PK data collected from period I to period IV. The possible case of the diet condition includes the following.

E: Dosing 2 hours after low-fat meal

F: Dosing 4 hours after light meal

G: Dosing 8 hours after low-fat meal

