7.1.2. Safety Assessments

7.1.2.1. Adverse Events

Adverse events will be coded according to the MedDRA version 22.0

(1) Adverse Events/ Serious Adverse Events (AEs/SAEs)

An AE/SAE is any untoward medical occurrence or unintended sign (including an abnormal laboratory finding), symptoms, and disease in a patient or subject who is administered a pharmaceutical product during safety assessment period, and which does not necessarily need to have a causal relationship with the treatment.

(2) Adverse Drug Reaction

A AE is considered “adverse drug reaction” if it has been assessed as having a “reasonable possibility” in relationship to the investigational product .

(3) Time to Adverse Events

Time to Adverse Events occurrence (days) = AE start date – date of first administration + 1

(4) Duration of Adverse Events

Duration of Adverse Events (days) = AE stop date – AE start date + 1

(5) Period of Adverse Events

Visit in Group 1	Visit in Group 2	Visit in Group 3	Visit in Group 4	For TFLs
From on or after administration date/time in Day 1 to before administration date/time on in day 3	From on or after administration date/time in Day 7 to before administration date/time on in day 23	From on or after administration date/time in Day 5 to before administration date/time on in day 7	From on or after administration date/time in Day 3 to before administration date/time on in day 5	Fasted
From on or after administration date/time in Day 3 to before administration date/time on in day 5	From on or after administration date/time in Day 1 to before administration date/time on in day 3	From on or after administration date/time in Day 7 to before administration date/time on in day 23	From on or after administration date/time in Day 5 to before administration date/time on in day 7	8 hours after high-fat meal
From on or after administration date/time in Day 5 to before administration date/time on in day 7	From on or after administration date/time in Day 3 to before administration date/time on in day 5	From on or after administration date/time in Day 1 to before administration date/time on in day 3	From on or after administration date/time in Day 7 to before administration date/time on in day 23	4 hours after low-fat meal

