From on or after administration date/time in Day 7 to before administration date/time on in day 23	From on or after administration date/time in Day 5 to before administration date/time on in day 7	From on or after administration date/time in Day 3 to before administration date/time on in day 5	From on or after administration date/time in Day 1 to before administration date/time on in day 3	2 hours after light meal
From on or after administration date/time in Day 23 to end of study assessment	From on or after administration date/time in Day 23 to end of study assessment	From on or after administration date/time in Day 23 to end of study assessment	From on or after administration date/time in Day 23 to end of study assessment	2 hours after low-fat meal

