8.3.1. Adverse Events

Overall summary for the following will be conducted by treatment.

- Subjects with at least one AE
- Subjects with at least one adverse drug reaction
- Subjects with at least one SAE
- Subjects with at least one serious adverse drug reaction
- Subjects with at least one AE leading to discontinuation of investigational product
- Subjects with AE leading to death

The following summaries also will be conducted by treatment.

- AEs by SOC and PT
- Adverse drug reactions by SOC and PT
- AEs by SOC, PT and severity

Each of the summaries will be done at the subject level - multiple occurrences of the same event within a subject will be counted once in the summaries by SOC and PT; multiple occurrences of the same event within a subject will be counted once in the maximum severity category (severe > moderate > mild) and/or maximum drug relationship category (reasonable possibility/no reasonable possibility) and/or the earliest duration.

All AEs will be listed.

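### Does the Day 23 label in the SAP's adverse-event table put events under the wrong meal condition?

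*SAP*

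**What the plan says.** SAP 7.1.2.1(5) has five rows, one per meal condition, and four columns, one per randomised group. Whichever condition a group receives in Period IV has the window "From on or after administration date/time in Day 7 to before administration date/time on in day 23". The Period V condition, a low-fat meal 2 hours before dosing, has the same window in all four groups: "From on or after administration date/time in Day 23 to end of study assessment".

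SAP 9.3 lists the visits for the safety summaries. Day 23 has laboratory tests, vital signs and ECG with no time point. Day 24 has pre-dose (marked as baseline) and 1 hour, Day 25 has 24 hours, and Day 26 has 48 hours with laboratory tests.

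The design table in SAP 3.2.1 places the last dose at "Period V (at Day X+1", and Protocol 8.6.1 defines "X = Day of hospital admission in period V". Dosing therefore falls on the day after admission. Neither document gives X as a number.

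The windows feed the summaries in SAP 8.3.1: "Overall summary for the following will be conducted by treatment".

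**The concern.** The table in 7.1.2.1(5) is the SAP's only stated rule for linking an adverse event to a meal condition. Under the 9.3 schedule, Day 23 is the admission day and nobody is dosed until Day 24. If the boundary were set at the calendar date of Day 23, an event starting between then and the Day 24 dose would be counted under the Period V meal before the subject had received it. It would also drop out of that subject's Period IV condition. The exposed interval is about 1 to 1.5 days, assuming the dose is given by midday.

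That interval is not an idle one. Admission includes laboratory tests, ECG, vital signs and a physical examination, and Protocol 9.2.5.2 dates a laboratory adverse event to the day of the test. A significant abnormality found at admission would therefore be dated Day 23.

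The label also does not look like a placeholder. The SAP already names the chosen Period V condition and reports the data review meeting of November 26, 2019 as past.

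**Working it through.** **Step 1: how far the label reaches.** The table has 5 rows × 4 groups = 20 cells. Day 23 appears in 4 cells as the end of the Period IV window and in 4 as the start of the Period V window. That is 8 cells and one boundary.

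**Step 2: which day the rest of the SAP implies.** Protocol 9.2.5.1 sets the Period V safety checks at X (admission, untimed, with laboratory tests), X+1 (pre-dose and 1 hour), X+2 (24 hours) and X+3 (48 hours, with laboratory tests). The table sets this against SAP 9.3.

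| Day | SAP 9.3 shows | Protocol if X = 23 | Protocol if X = 22 |
|---|---|---|---|
| 23 | untimed, laboratory tests | X: untimed, laboratory tests | X+1: pre-dose, 1 h |
| 24 | pre-dose, 1 h | X+1: pre-dose, 1 h | X+2: 24 h |
| 25 | 24 h | X+2: 24 h | X+3: 48 h, laboratory tests |
| 26 | 48 h, laboratory tests | X+3: 48 h, laboratory tests | nothing scheduled |

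X = 23, with the dose on Day 24, fits 4 of 4 days. X = 22, which would make Day 23 the dosing day, fits 0 of 4. The other administration days in the adverse-event table (1, 3, 5 and 7) each have a pre-dose row in 9.3, and Day 23 does not.

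The planned gap between Period IV discharge and Period V admission does not help. Protocol 5.2.2 allows 11 to 18 days after Day 9, so X runs from 9 + 11 = 20 to 9 + 18 = 27. Both X = 22 (13 days) and X = 23 (14 days) qualify. Day 24 is therefore a strong inference from the visit pattern, and the dosing records would settle it.

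**Step 3: whether the label moves any event.** Each cell sets its limits by the date and time of an administration.

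- Protocol 8.4 gives one dose per period, so only one administration can open the Period V window.
- Protocol 9.2.3 says staff "will record the date and time of investigational product administration in the CRF", so the limit is an observed value.
- An event dated Day 23 lies before a Day 24 dose on its date alone, whether it began before or after admission.
- An event dated Day 24 needs a clock time. The subject is then in hospital (Protocol 8.6.1), and Protocol 9.2.5.2 requires onset time for every adverse event during hospitalization.

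Comparing onset with the recorded Period V dose therefore assigns every event correctly, whichever day number is printed.

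**Step 4: what else uses the boundary.** Nothing in the food-effect analysis (SAP 8.4.2) does. Laboratory summaries are by group and visit, with a baseline before the first dose. Vital-sign and ECG baselines are the last values before the dose in each period, and 9.3 places the Period V one on Day 24.

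**The case for a change.** The strongest case for a correction is that the two tables cannot both be right, that the SAP states it takes precedence over the protocol's description of the analysis, and that a programmer reading the cell literally is sent to a day with no dose. Putting it right would cost one label and one program check.

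The disagreement itself stands. The harm does not follow from it. A program that searched for an administration on Day 23 would find none for any subject, so the Period IV windows would have no end and the Period V window no start. That would be hard to miss. Events are misplaced silently only if the programmer discards the administration time and substitutes a calendar date, which departs from the SAP's wording. The same shortcut would also blur the boundaries on Days 3, 5 and 7, where the labels are correct. The precedence clause does not change this, since the SAP's own design table also puts the dose on the day after admission.

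SAP 9.3 is not flawless either. It labels Day 9 as 46 hours for everyone, although the protocol uses 46 hours in Periods I to IV only for the condition dosed 4 hours after a low-fat meal. That is an error in an hour label and does not disturb the day sequence used above.

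Adverse-event rates from the earlier oral studies could be used to guess how many events fall in the interval. Those studies used other doses and designs, and the guess would need events spread evenly over time, which is doubtful when admission is itself a test day. Such a figure would not be evidence, so none is offered.

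**Conclusion.** This is a clerical slip that calls for no change to the plan. One day label, repeated in eight cells, is very probably the admission day written where the dosing day belongs. The operative rule is the recorded administration time, and it identifies a single dose per subject.

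The expected effect is no change in any adverse-event or adverse-drug-reaction count by condition, and no effect on any pharmacokinetic, laboratory, vital-sign or ECG result. This rests on the program comparing event onset with the recorded Period V administration date and time, as the cells say. If a calendar cut-off on Day 23 were used instead, only events starting between that date and the dose could move, and only in descriptive tables. SAP 8.3.1 requires every adverse event to be listed, so a moved event could be traced. The documents report no event in that interval.

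Confidence is high that the two tables disagree, moderate to high that the dose fell on Day 24, and low that any reported count depends on it.

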7.1.2.2. Laboratory Tests

Values for out of pre-defined clinically relevant will have clinically relevant values flagged set (L=Lower than normal range, H=Higher than normal range or A=Abnormal).

7.1.2.3. 12-Lead ECG

(1) Criteria for pre-defined limit

12-lead ECG:

- QTcF > 500msec
- $500 \geq QTcF > 480$ msec
- $480 \geq QTcF > 450$ msec
- QTcF ≤ 450 msec
- Change from baseline in QTcF > 30 msec
- Change from baseline in QTcF > 60 msec

7.1.3. Pharmacokinetics Evaluation

7.1.3.1. Plasma Concentration

For the calculation of the summary statistics, concentration values reported as below the limit of quantification (BLQ) will be set to 0.

7.1.3.2. Pharmacokinetic Parameters

Below the limit of quantification

For the calculation of PK parameters, actual sampling time (in hours rounded to 3 DPs) relative to dosing should be used. Concentration below the limit of quantification (BLQ) will be imputed with a value of 0. For calculation of AUCs, missing data will be treated as if the respective sample never had been scheduled for the calculation by the linear-linear trapezoidal rule. For Ae, Ae% and CLr, geometric mean and geometric CV% will be calculated only when all the individual Ae, Ae% and CLr is greater than 0 in each sampling time point.

7.2. Analysis Visit Definitions

(1) Non-PK related

The date of the first dose of investigational product is defined as Day 1.

Excepted for laboratory, baseline will be the last observed value of the parameter of interest prior to the first intake of investigational product by each treatment period (this includes unscheduled visits). For laboratory, baseline will be the last observed value of the parameter of interest prior to the first intake of investigational product (this includes unscheduled visits).

No analysis visit window will not be perfomed for safety evaluation.

(2) PK related

The allowable time window will be the following.

Plasma PK sampling

Nominal Time Point	Window
Predose	Within 60 min before dosing
0.083 h after dosing	Nominal time point \pm 1 min
0.25, 0.5, 0.75, 1, 1.5, 2, 4, 6, 8, 10, 12 h after dosing	Nominal time point \pm 5 min
24, 36 h after dosing	Nominal time point \pm 15 min
48 h* after dosing *Following the dosing 4 hours after meals, blood sampling is conducted 46 h after dosing	
Blood sampling 46 h after dosing	[Period I, II, and III] 45~47 h after dosing and within 60 min before the dosing in the next period [Period IV and V] 45~47 h after dosing
Blood sampling 48 h after dosing	[Period I, II, and III] 47~50 h after dosing and within 60 min before the dosing in the next period [Period IV and V] 47~50 h after dosing

Urine PK sampling

Nominal Time Point	Window
Predose	Within 60 min before dosing
Voluntary Urine	—
Forced micturition at 24 h after dosing	Nominal time point \pm 30 min

Nominal Time Point	Window
Forced micturition at 48* hours post-dose * Forced micturition at 46 h post-dose for subjects dosed 4 h after meals	
Forced micturition at 46 h after dosing	[Periods I, II, and III] 45~47 h after dosing and within 60 min before the dosing in the next period [Periods IV, V] 45~47 h post-dose
Forced micturition at 48 h after dosing	[Periods I, II, and III] 47~50 h after dosing and within 60 min before the dosing in the next period [Periods IV, V] 47~50 h post-dose

7.3. Data Handling Convention for Missing Data

(1) Non-PK related

Adverse events:

If severity or relationship is found to be missing the most severe occurrence will be imputed for the summary of interest.

Other safety:

For safety summaries, only observed data will be used. Unless otherwise specified, missing safety data will not be imputed.

(2) PK related

For PK summaries, only observed data will be used. Missing PK data will not be imputed. When calculating Ae and Ae%, missing PK data will be imputed to 0.

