Based on the results of the Phase I clinical pharmacology studies (MT-1186-J01 and MT-1186-J02), time points of blood sampling were set with reference to "Clinical Pharmacokinetic Studies of Pharmaceuticals" [3].

9.2.4.2 Measurement of urine concentrations of unchanged edaravone, sulfate conjugate, and glucuronide conjugate

Urine volume will be measured at voiding and the urine specimen will be processed (see Section 9.2.4.3). The urine is forced to void before administration as well as 24 and 48 hours after administration (46 hours after administration in the conditions C [dosing 4 hours after low-fat meal] and F [dosing 4 hours after light meal]).

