9.2.4.3 Processing and storage of specimens

(1) Specimens for measurement of plasma concentrations of unchanged edaravone, sulfate conjugate, and glucuronide conjugate

Promptly after drawing roughly 5.5 mL of blood from the vein into a vacuum tube with heparin sodium, gently invert the tube several times. The subsequent procedures should be performed on ice and completed within 120 minutes after the blood sampling. Transfer the blood into tubes with a stabilizer that has been supplied by the sponsor, and centrifuge the tubes at 4°C, 1,500 g for 10 minutes, so as to complete the centrifugation within 30 minutes after blood sampling. Accurately place the specified amount of plasma into tubes (the primary specimen and backup specimen) with the fixed amount of internal standard, stabilizer, and buffer that has been supplied by the sponsor and store them at -70°C or below. Additional details regarding the procedure are specified in a separate procedure.

Pack the primary specimen and send it in a frozen state with a sufficient amount of dry ice to [REDACTED]. At the request of the sponsor, send the backup specimen, as well.

(2) Specimens for measurement of urine concentrations of unchanged edaravone, sulfate conjugate, and glucuronide conjugate

Collect voluntary urine and measure its volume. Accurately put the specified amount of the urine into test tubes (the primary specimen and backup specimen) containing the fixed amount of stabilizer provided by the sponsor, and store them at -70°C or below. Additional details regarding the procedure are specified in a separate procedure.

Pack the primary specimen and send it in a frozen state with a sufficient amount of dry ice to [REDACTED]. At the request of the sponsor, send the backup specimen, as well.

[Specimen shipping address]
[REDACTED]
[REDACTED]

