13.3 Data Handling

The data will be handled as described below, except for cases determined in the sponsor's data review meeting or at the meeting for the handling of drug concentration data. The handling of the safety and drug concentration data will be specified in the Statistical Analysis Plan or the Clinical Study Report.

(1) Handling of PK data

The acceptance time range for each blood sampling timepoint for determining the plasma drug concentrations will be specified in the Statistical Analysis Plan. The sponsor will judge the handling of the following data, as to whether or not to include them in the tabulation and analysis of the drug concentrations: (1) data that was collected from a blood specimen drawn outside of the acceptance time range; (2) data for which the plasma drug concentration was unmeasurable; and, (3) data for which a protocol deviation occurred, such as non-compliance with plasma collection procedures. The handling of data will be decided at the data review meeting or at the conference for the handling of PK data.

(2) Handling of analysis data for each time point

The acceptable time range for each measurement time point will be specified in the Statistical Analysis Plan, and the data collected within the time range will be used. Data will not be imputed by data collected outside the time range. If multiple data exist within the same time range for one assessment item, the data collected later will be used.

(3) Handling of unmeasurable data and reference data in laboratory tests

If unmeasurable or reference data are obtained due to specimen problems, etc., they will be handled as missing data.

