8.3.5. Physical Examinations	23
8.4. Pharmacokinetics Evaluation.....	23
8.4.1. Concentrations and Pharmacokinetic Parameters for unchanged edaravone, sulfate conjugate, and glucuronide conjugate	24
8.4.2. Analysis of Food Effect.....	24
9. DATA PRESENTATION CONVENTIONS	25
9.1. Number of Digits to Report	25
9.2. Treatments to Report.....	26
9.3. Analysis Visits to Report	26
10. CHANGE FROM THE PROTOCOL	27
11. SOFTWARE.....	27
12. REFERENCES	27

ABBREVIATIONS

Abbreviations	Definitions
AE	adverse event
ALT	alanine transaminase
ALP	alkaline phosphatase
AST	aspartate transaminase
ATC	anatomical therapeutic chemical
BLQ	below limit of quantification
BMI	body mass index
CI	confidence interval
CV	coefficient of variation
DP	decimal places
DRM	data review meeting
ECG	electrocardiogram
MedDRA	medical dictionary for regulatory activities
PK	pharmacokinetics
PT	preferred term
SAP	statistical analysis plan
SAE	serious adverse event
SAF	safety population
SD	standard deviation
SOC	system organ class
WHO	World Health Organization

LIST OF PK PARAMETERS

Parameters	Definitions
AUC_{0-24}	Area under the plasma concentration-time curve from zero up to 24 hour
AUC_{0-t}	Area under the plasma concentration-time curve from zero up to the last quantifiable concentration time point
$AUC_{0-\infty}$	Area under the plasma concentration-time curve from zero up to infinity with extrapolation of the terminal phase
$AUC\%_{ex}$	Area under the (plasma) concentration-time curve extrapolated from the last quantifiable concentration time point to infinity in % of the total $AUC_{0-\infty}$
Ae_{0-24}	Cumulative urinary excretion amount of drug from zero to 24 hour
Ae_{0-48}	Cumulative urinary excretion amount of drug from zero to 48 hour
C_{max}	Maximum plasma concentration after administration
C_{last}	Last quantifiable concentration
CL/F	Apparent total clearance
CL_r	Renal clearance
Kel	Elimination rate constant from the central compartment
$LLOQ$	Lower limit of quantification
LOQ	Limit of quantification
MRT	Mean residence time
NC	Not calculated
$t_{1/2}$	Terminal elimination half-life in plasma concentration-time course
V_{ss}/F	Apparent volume of distribution at steady state
V_z/F	Apparent volume of distribution during terminal phase
$Ae\%$	Urinary excretion ratio of drug

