9. DATA PRESENTATION CONVENTIONS

9.1. Number of Digits to Report

(1) Non-PK related

Statistic	Specification	Apply to
Minimum, Maximum	Same number of DPs as the data provided in the datasets	All original (i.e. non-derived)
	see section 7.3	All derived data
Mean, Median, SD, SE, Confidence intervals	One more DP than above	All
Percentages ^{*1}	1 DP	All

*1 Percentages: use 1 place beyond the decimal point, except for the following cases:

If the percentage is equal to 0, then leave blank, do not use (0)

If the percentage is equal to 100, then use "(100)" without a decimal

(2) PK Plasma Concentration

Statistic	Specification
Individual value	With the number of DPs to which they are reported
Mean, SD, Minimum, Median, Maximum	Same number of DPs as the individual value

(3) PK Parameters

Plasma PK Parameters

Statistic	Specification
Individual value	C_{max} : same number of DPs as the plasma concentration t_{max}^* : 2 DPs Kel: 4 DPs Other parameters to be summarized: number of DPs which the number of significant digits of a minimum parameter is three $AUC\%_{ex}$: 2 DPs Adjusted R^2 : 2 DPs Number of Kel points: 0 DP Lower and Upper limited of Kel: 2 DPs
Mean, SD, Minimum, Maximum, Median, Geometric mean	Same number of DPs as the individual values
CV%, Geometric CV%	1 DP
Ratios	3 DPs

*: t_{max} will be expressed basically in terms of median and range

Urine PK Parameters

Statistic	Specification
Individual value	$Ae, Ae\%$: 3 DPs

	CLR: number of DPs which the number of significant digits of a minimum parameter is three
Mean, SD, Minimum, Maximum, Median, Geometric mean	For Unchanged Edaravone: 3 DPs For Sulfate Conjugate: 2 DPs For Glucuronide Conjugate: 1 DP For Sum of Unchanged Edaravone and Metabolites: 1 DP
CV%, Geometric CV%	1 DP

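### SAP 7.3(2) sets every missing urine value to zero for Ae and Ae%, which biases recovery and renal clearance downward when a void was passed but its volume or concentration is missing

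*SAP*

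**What the plan says.** SAP 7.3(2) first says that PK summaries rest on observed values without imputation. It then makes one exception: "When calculating Ae and Ae%, missing PK data will be imputed to 0". No condition is attached.

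The related rules are these:

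- **BLQ.** SAP 7.1.3.2 has a separate rule: "Concentration below the limit of quantification (BLQ) will be imputed with a value of 0". The sentence in 7.3(2) therefore governs values that are truly missing.
- **Missing plasma samples.** For AUC, SAP 7.1.3.2 drops a missing sample from the calculation and does not set it to zero.
- **Definition of Ae.** SAP Appendix 1 defines Ae as urine concentration times urine volume. The SAP list of PK parameters makes it cumulative, with the 24-hour version defined as "Cumulative urinary excretion amount of drug from zero to 24 hour" and a matching 48-hour version.
- **Collection.** Protocol 9.2.4.2 works void by void: "Urine volume will be measured at voiding and the urine specimen will be processed". Protocol 9.2.4.3 says the same of voluntary urine: "Collect voluntary urine and measure its volume".
- **Reporting.** SAP 8.4.1 lists and summarises the urinary parameters for each treatment. SAP 9.1 also sets a urine reporting format for total recovery: "For Sum of Unchanged Edaravone and Metabolites: 1 DP".

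**The concern.** A missing value in a void-by-void collection can arise in two ways. The subject may have passed no urine, for example at a forced time, and then the amount excreted really is zero. Or a void was passed and its volume or assay result is not available, and then the amount is unknown and in general positive. The rule gives both the same answer.

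In the second case lost data would appear as lower urinary recovery, and for unchanged edaravone as lower renal clearance, for one subject under one meal condition. The study exists to compare meal conditions, so a reader of the urinary tables could take a collection or assay gap for a difference between conditions. A missing volume affects all three analytes in that void, while a failed assay affects one. Either also lowers the summed recovery of edaravone and its metabolites.

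**Working it through.** The plan gives no figure to reproduce here. The check is algebra on the SAP's own formulas, followed by an illustration on stated assumptions.

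**Inputs from the documents**

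- Ae = sum over voids of concentration × volume; Ae% = Ae / Dose; CLr = Ae / AUC0-∞ (SAP Appendix 1 and list of PK parameters).
- CLr is listed for unchanged edaravone only (SAP 2.2.2).
- There are 16 subjects, and each receives every condition (SAP 3.2.1 and 3.4).

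**Direction of the error**

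Let f be the share of a subject's true cumulative Ae, in the window concerned, that lies in the void with the missing value. Setting that void's concentration or volume to zero removes a term that cannot be negative, so

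reported Ae / true Ae = 1 − f.

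Dose is fixed and AUC0-∞ comes from plasma, so Ae% and CLr carry the same factor 1 − f. The error cannot be upward. It is nil only if the lost void held no quantifiable drug or was the pre-dose void, which is not summarised. If no urine was passed, the volume is zero, the term is truly zero and there is no bias.

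**Size in a condition summary**

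The documents give no per-void amounts, so f is an assumption, as is one affected subject in 16. The affected subject's true value is taken as equal to the mean (arithmetic or geometric) of the condition.

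- Fall in arithmetic mean = f / 16
- Fall in geometric mean = 1 − (1 − f)^(1/16)

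| f (assumed) | Fall in subject's Ae, Ae%, CLr | Fall in arithmetic mean | Fall in geometric mean |
|---|---|---|---|
| 0.10 | 10% | 0.10/16 = 0.6% | 1 − 0.90^(1/16) = 0.7% |
| 0.25 | 25% | 0.25/16 = 1.6% | 1 − 0.75^(1/16) = 1.8% |
| 0.50 | 50% | 0.50/16 = 3.1% | 1 − 0.50^(1/16) = 4.2% |

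In the extreme case all of a subject's urine values in a window are missing. Ae becomes 0 and the arithmetic mean falls to 15/16 = 0.9375 of its true value. SAP 7.1.3.2 then suppresses the geometric statistics, because "geometric mean and geometric CV% will be calculated only when all the individual Ae, Ae% and CLr is greater than 0". That condition does not catch a partial loss, since the subject's value stays above zero and enters the summary unmarked.

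**The case against.** The strongest reply is that nothing shows the rule was ever applied to a passed void.

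- **Data review meeting.** SAP 6.3 reports in the past tense that no protocol deviation was observed and that all PK data were considered valid. A passed void without a volume or specimen would breach Protocol 9.2.4.2 and 9.2.4.3. That leaves mainly an assay failure on a collected specimen.
- **Backup specimen.** Protocol 9.2.4.3 stores a primary and a backup urine specimen, so a failed primary assay need not leave a missing result.
- **Meeting override.** Protocol 13.3 allows exceptions to its data-handling rules for cases settled at the data review meeting "or at the meeting for the handling of drug concentration data".
- **Likely intent.** Voluntary voids have no nominal time in SAP 7.2, so the missing record to be expected is a forced time with no urine, where zero is right.

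Most of this stands as a reason to expect little or no actual effect, but it does not make the rule correct. Data judged valid are not the same as no data missing, and SAP 6.3 does not say that no urine value was missing. The backup specimen makes a missing concentration rarer without excluding it. The PK cases listed in Protocol 13.3(1) concern blood specimens and plasma concentrations, and SAP section 1 says that its analysis details supersede the protocol's. If the intent was to cover only intervals without urine, the sentence needs to say so.

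**Conclusion.** The concern holds. As written, the rule gives a wrong, downward-biased result whenever a passed void that contained quantifiable drug has a missing volume or concentration. The direction follows from the SAP formulas and needs no assumption. The size does: the falls of 0.6% to 3.1% in the arithmetic mean and 0.7% to 4.2% in the geometric mean rest on an assumed f of 0.10 to 0.50 in one of 16 subjects.

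The point is minor. It touches only descriptive secondary urinary summaries. The food-effect ANOVA in SAP 8.4.2 uses plasma Cmax and AUC and is not affected. The documents do not show that any urine value was lost.

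**What to change.** Reword SAP 7.3(2) along these lines:

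1. Use zero for a void or interval only when no urine was passed, or when the measured concentration is BLQ (as 7.1.3.2 already provides).
2. If a void was passed and its volume or concentration is missing, flag and list as incomplete every cumulative Ae, Ae%, CLr and summed recovery whose window includes that void, and leave those values out of the summary statistics. A void lost after 24 hours leaves Ae0-24 usable.
3. State whether any urine value was missing. If none was, one line to that effect removes the doubt for this dataset.

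The cost is one SAP sentence and a programming flag. The drawback is that n falls by one per affected subject in that summary, even if the lost void was small. From 16 to 15 the standard error of the mean rises by a factor of √(16/15) = 1.033, about 3.3% at unchanged SD. Listing the incomplete values keeps them visible as lower bounds.
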